Association between the Irrigation-Agitation Techniques and Periapical Healing of Large Periapical Lesions: A Randomized Controlled Trial

Clinical Trial Number: NCT06204887

Date: 16.05.2024

STUDY PROTOCOL

Local ethics committee approval was obtained from the Ethical Review Committee of the Research Foundation at the Medical Faculty of Recep Tayyip Erdogan University (No: 2023/35) and the study protocol was registered at ClinicalTrials.gov (NCT06204887).

Sample size calculation

The G Power 3.0.10 (University Kiel, Germany) program was used to calculate the effect size. The effect size was calculated based on chi-square analysis data between the control group and the laser group in the Verma, Yadav study [26]. An effect size of 0.51 Cohen d value was found to be sufficient for significance. With a type 1 error of 0.05, it was determined that at least 56 subjects were required for a total of 4 groups, 14 in each study group, with 95% power.

Patient Recruitment and Randomization

Patients were informed about the procedure, and written informed consent was obtained before the commencement of treatment. The study included mandibular single-rooted teeth that were diagnosed with asymptomatic apical periodontitis and had a periapical index (PAI) score of 3 or higher. A total of 97 patients aged 18-65 were evaluated radiographically and clinically for conformity with the inclusion and exclusion criteria. Patients with systemic diseases (diabetes, hypertension, chronic liver disease, coagulation disorders), bone metabolism disease and/or patients using drugs that affect bone metabolism (such as steroids and bisphosphonates) were excluded from the study. Immunosuppressed patients, patients with a history of radiotherapy, pregnant patients, patients with teeth with a mobility of 2 or more (Miller's mobility index), patients with teeth with a periodontal pocket depth of 5 mm or more, patients with generalized asymptomatic apical periodontitis, patients with teeth with internal and external resorption, and patients with teeth with vertical and horizontal root fractures were not included.

After applying the eligibility criteria, 70 patients were randomly divided into four groups using software (www.random.org) by a blinded researcher who was not otherwise involved in the study according to a standardized procedure. The numbers were placed in dark envelopes and concealed. The envelopes were only opened when the irrigation solution was to be activated. The patients were informed about the study without specifying the group to which they were assigned. All procedures were performed by a single operator with five years of experience ([name]).

CBCT imaging (Planmeca Romexis, Helsinki, Finland) was requested for patients who met the study criteria before the procedure to obtain information about periapical lesion size, proximity to anatomical landmarks, and anatomical variations of the tooth. CBCT images were acquired with a field of view (FOV) of 5×5 cm using ENDO mode, an 85 µm voxel size, 6.3 mA, 90 kV, and 8.7 s.

Clinical procedures

A CONSORT flow diagram outlining the treatment methodology is presented in Figure 1. After the administration of local anesthesia and the placement of a rubber dam, the access cavity was opened with a sterile diamond round bur under water cooling. Each canal was rinsed with 2 mL of sodium hypochlorite and explored with a size 08 K-file (FKG Dentaire, La Chaux-de-Fonds, Switzerland). The working length was determined using an electronic apex locator, Root ZX mini (J. Morita Co., Tokyo, Japan), to be 0.5 mm shorter than a 0.0 reading. The length was confirmed radiographically. After that, progressively larger K-files were passively introduced into the canal until the operator felt the first one to bind at the WL and the next larger one not to reach that position [27]. The first instrument used to bind the canal was recorded for each canal. The crown-down technique was applied with ProTaper Next rotary files (Dentsply Maillefer, Ballaigues, Switzerland) using a torque-controlled endodontic motor (SybronEndo, Glendora, CA, USA) at 300 rpm/2-5.2 Ncm rotation mode according to the manufacturer's instructions. The final instrumentation file was set to 3 sizes larger than the first file used[28]. Between each instrument change, the root canal was irrigated with 5 mL of 2.5% NaOCl (Microvem AF, Istanbul, Turkey) for 1 min. After canal preparation was completed, the final irrigation procedure was carried out with the corresponding irrigation method in each group.

[figure not shown]

Figure 1. Consolidated Standards of Reporting Trials (CONSORT) flow diagram for patients included in this study.

Control Group: Conventional Syringe Irrigation

A 30-gauge side-vented irrigation needle (Kerr Hawe Sa, Bioggio, Switzerland) was used. The needle was inserted into the canal 1 mm shorter than the working length, and the canal was irrigated with up-and-down movements of 1-2 mm amplitude using the same and constant average pressure. The irrigation protocol was performed with 6 ml of 17% EDTA followed by 6 ml of 2.5% NaOCl for 1 min. Between each cycle, 5 ml of distilled water was used to prevent chemical interactions.

Group 1: Manual Dynamic Activation (MDA)

After the root canal preparation was completed, the final irrigation was started, the main gutta percha cone was positioned 1 mm shorter than the working length, and a 2 mm coronal-apical movement was performed at a speed of 100 strokes/minute for 60 seconds. The irrigation protocol was performed with 6 ml of 17% EDTA followed by 6 ml of 2.5% NaOCl for 1 min. Between each cycle, 5 ml of distilled water was used to prevent chemical interactions.

Group 2: Passive Ultrasonic Irrigation (PUI)

In this group, a noncutting ultrasonic tip (IRRI S 21/25; VDW, Munich, Germany) coupled to an ultrasonic device (DTE S6 Led, Guilin Woodpecker Co., Guilin, Guangxi, China) (mode: E, setting: 6) was used according to the manufacturer's recommendations.

The tip was positioned 2 mm short of the working length without contacting the walls. Continuous irrigation was performed using 2 ml of 17% EDTA followed by 2 ml of 2.5% NaOCl with activation 3 times for 20 seconds. To prevent chemical interactions between NaOCl and EDTA, 5 ml of distilled water was used between each irrigant. In total, 1 min of irrigation activation was carried out.

Group 3: Laser-Activated Irrigation (SWEEPS)

In this group, a 2940 nm Er:YAG laser device (Lightwalker, Fotona, Ljubljana, Slovenia) equipped with a handpiece (H14, Fotona) holding an 8.5 mm long and 600 μ m diameter tapered fiber tip (SWEEPS 600, Fotona) was used for irrigation activation. The device was set to AutoSWEEPS mode with two ultrashort micropulses (25 μ s) continuously varying at 0.3 W, 20 mJ, and 15 Hz. The air and water sprays were turned off.

A 30-gauge side-perforated irrigation needle (Kerr Hawe Sa, Bioggio, Switzerland) was inserted 1 mm shorter than the working length, and the fiber tip was positioned in the center of the access cavity and fixed in this position. Then, 2 ml of 17% EDTA was activated 3 times for 20 s. The same procedure was repeated with 2 ml of 2.5% NaOCl solution by flushing distilled water between each irrigant as described before.

After the final irrigation procedures, the root canals were dried with 25/.06 paper cones (DiaDent, Heungdeok-gu, Korea), and the cold lateral compaction obturation technique with a root canal sealer (Meta Biomed, Cheongju, Güney, Korea) was used to fill all the canals. Permanent restoration was performed directly with composite resin material (Palfique Estelite, Tokuyama Dental Co., Tokyo, Japan).

Follow-up procedures

For routine follow-up, 2D radiographs were taken at 3, 6, and 9 months, as well as via intraoral examinations. Radiographic healing in both 2D and 3D at baseline and at a follow-up of 1 year was assessed by a calibrated evaluator who was blinded to the allocation group. The teeth were assessed for reported symptoms, sensitivity to palpation and percussion, mobility and probing depth. The presence of failure (intraoral swelling or sinus tract) was recorded.

Healing evaluation: lesion area and volume calculation

Twelve months after the root canal treatment, new CBCT images were taken with the same device (Planmeca Promax 3D Classic device (Planmeca Romexis, Helsinki, Finland)) and the same parameters (85 μ m voxel size, 6.3 mA, 90 kV, 8.7 with FOV area 5x5 cm).

3D lesion volume calculation was performed using ITK SNAP (free software under the GNU General Public License developed by the National Institutes of Health, the US National Institute of Biomedical Imaging and Bioenergy needs, the US National Library of Medicine, the Universities of Pennsylvania and North Carolina, and an independent group of developers) by an oral maxillofacial radiologist with 12+ years of experience.

The preoperative and 1-year postoperative CBCT images of the patients were measured following the same steps in the ITK-SNAP program. We used the same techniques used by Schloss et al[15]. First, the captured CBCT images were exported in DICOM file format from the Planmeca Romexis software. The exported images were then opened with ITK-SNAP software. Using the highest resolution allowed by the captured CBCT images (0.09 mm), the slice thickness and slice interval were set to 0.09 mm. The ITK-SNAP program includes a semiautomatic segmentation feature, which was utilized. In this feature, automated spherical fillers, or bubbles, as referred to in the program, were placed according to the grayscale of the lesion. Repeated runs were performed until the entire area of the lesion was filled, with the bubbles placed in the lesion area. After the internal area of the lesion was completely filled, the images were evaluated from axial, sagittal, and coronal sections to correct any possible overfilling or underfilling situations due to artifacts from canal filling materials using a manual marker. The volume of the painted area obtained was calculated in mm³ using the program's feature. The evaluation of the tomography images obtained before and after treatment was conducted at one-month intervals. The images were provided to the evaluators in a randomized manner.

The volume data were compared with the preoperative CBCT measurements for each patient. The volume changes were measured, and the long-term outcomes of the procedures were compared.

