Association between the Irrigation-Agitation Techniques and Periapical Healing of Large Periapical Lesions: A Randomized Controlled Trial

Clinical Trial Number: NCT06204887

Date: 16.05.2024

Statistical analysis

Analyses were carried out in the IBM SPSS 25 program. As the first step of the statistical analysis, the normality of the data was checked with the Shapiro–Wilk test. When normality was ensured, the Wilcoxon signed rank test was applied to examine the difference between the means of two dependent groups. ANOVA was used to examine the difference between the means of three or more independent groups. In cases where the data were not normally distributed, the Kruskal–Wallis test was performed. The post hoc Bonferroni correction was used to determine the group or groups that were significantly different.

Pearson's chi-square test was applied to examine the relationships between study groups and sex. The Kruskal–Wallis test was applied to examine the differences between the average ages of the participants in the study groups. Spearman correlations were used to control for the relationships between age and lesion volume measurements obtained at different times and from different study groups. To compare lesion volume measurements according to study group at different measurement times, ANOVA and the Kruskal–Wallis test were applied. Bonferroni correction were performed to compare the groups. Wilcoxon signed rank tests were used to compare lesion volume measurements according to different measurement times in the study groups.

For comparisons of lesion volume measurements at different measurement times in the study groups, assumptions were checked, and Wilcoxon signed-rank tests were used. Analyses were performed with the IBM SPSS 25 (SPSS Inc., Chicago, IL) program. The Pearson chi-square test was used to examine the relationships between study groups and sex. The Spearman correlation test was used to assess the relationships between lesion volume measurements obtained at different times and study group and age.

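### The 95% power is stated at an uncorrected 0.05, but the SAP identifies differing techniques only after Bonferroni correction; at the printed 0.51 and 14 per group that comparison misses 95% under every reading tried

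*Protocol*

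**What the plan says.** Protocol, 'Sample size calculation': the source of the effect is "The effect size was calculated based on chi-square analysis data between the control group and the laser group" of a cited study, whose rates are not given. The paragraph continues: "An effect size of 0.51 Cohen d value was found to be sufficient for significance". The alpha and size follow: "With a type 1 error of 0.05, it was determined that at least 56 subjects were required for a total of 4 groups", completed by "14 in each study group, with 95% power". It mentions no multiplicity adjustment and no sidedness. It does not say whether the 95% belongs to the control-versus-laser contrast or to a test across all four groups.

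Protocol, 'Patient Recruitment and Randomization': "70 patients were randomly divided into four groups using software". The text gives no allocation ratio.

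SAP, 'Statistical analysis': the between-group test is an omnibus one: "To compare lesion volume measurements according to study group at different measurement times, ANOVA and the Kruskal–Wallis test were applied". The step that names the differing techniques is: "The post hoc Bonferroni correction was used to determine the group or groups that were significantly different". The number of comparisons is not given, and no contrast is named as primary or exempted. The Wilcoxon signed-rank tests compare time points within a group, so they cannot supply a comparison between techniques.

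**The concern.** The sizing takes its effect from one pair of arms and uses the full 0.05. The SAP declares that a technique differs from another only after dividing that 0.05 among several comparisons. The alpha behind the stated power is therefore not the alpha of the rule that answers the question of interest, namely which technique heals better than syringe irrigation.

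The stake is how a null result is read. Someone relying on the 95% would treat a non-significant laser-versus-control comparison as strong evidence that the planned effect is absent. Under the SAP's rule, the chance of missing that effect at 14 per arm is larger than the 5% implied.

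**Working it through.** **Inputs.** From the protocol: alpha 0.05, effect 0.51 (labelled Cohen d), n = 14 per arm, N = 56, four groups, 70 randomised. From the SAP: Bonferroni post hoc comparisons. Assumed, because not stated: two-sided tests, normal data, equal variances, and either six comparisons (all pairs, 0.05/6 = 0.0083) or three (each technique against control, 0.05/3 = 0.0167).

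**Step 1: the plan's own figure.** I tried to recover 95% at N = 56 with no correction.

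- 0.51 as d, two arms of 14: t-test power is 26%; 95% would need 101 per arm.
- 0.51 as f, four-group ANOVA: noncentrality 56 × 0.51² = 14.57 on 3 and 52 df gives 88%; 95% needs N = 71 (72 if balanced).
- 0.51 as w, 4 × 2 chi-square (df 3), N = 56: 91%; 95% needs N = 67.
- 0.51 as w, df 1, the two arms only: noncentrality 28 × 0.51² = 7.28 gives 77%.
- 0.51 as w, df 1, N = 56: 97%, but this is a two-group test with 28 per arm, and 95% would need N = 50. With df 2 the power is 94% and the required N is 60; df 2 does not fit four groups by two outcomes.

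Some power figures come near 95%, but no reading returns a required N of 56.

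**Step 2: control versus laser under the SAP's rule.** For the f and d readings I used the noncentral t with df = 4n − 4 = 52 and noncentrality d√(n/2) = d√7. Critical values are 2.007 (0.05), 2.474 (0.05/3) and 2.743 (0.05/6). For four groups, f converts to the difference between the extreme arms as follows:

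- other arms midway: d = f√8 = 1.44
- arms equally spaced: d = f√7.2 = 1.37
- arms split two and two: d = 2f = 1.02

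The w reading uses noncentral chi-square, df 1, noncentrality 7.28.

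| Reading of 0.51 | 0.05 | 0.05/3 | 0.05/6 |
|---|---|---|---|
| f, control and laser extreme, others midway | 96% | 91% | 85% |
| f, equally spaced | 94% | 87% | 81% |
| f, split two and two | 75% | 59% | 49% |
| w, 28 patients | 77% | 62% | 52% |
| d, as printed | 26% | 14% | 9% |

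**Step 3: grant the 95%.** Suppose the contrast does have 95% power at 0.05. With pooled df 52 that means d = 1.39. At 0.05/3 the power becomes 88%, and at 0.05/6 it becomes 82%. This result does not depend on what 0.51 means.

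**Step 4: the 70 randomised.** Taking 17.5 per arm (equal arms, all analysed), the six-pair figures in the order of the table are 94%, 90%, 62%, 65% and 12%. With three comparisons, the most favourable reading reaches 96%.

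**Step 5: detectable difference.** Solving the Step 2 formula for d at 0.05/6:

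| n per group | 80% power | 95% power |
|---|---|---|
| 14 | 1.36 | 1.68 |
| 17 | 1.23 | 1.51 |

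**The case against.** **The 95% may not be a pairwise claim.** The protocol attaches it to a total across four groups, and powering an omnibus test before corrected post hoc comparisons is common practice. This stands in part: the paragraph does not say which test is meant. But its effect comes from a single pair, and if the ANOVA was intended with f = 0.51, the power is 88%, not 95%.

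**Six comparisons is an assumption.** This stands. The SAP gives no count, and a design with one control and three techniques could be read as three comparisons. Both counts are therefore shown.

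**85% is not a ceiling.** A reader might infer from the table that corrected power is at most about 85%, that the shortfall is always at least 10 points, or that the miss rate at least triples. The documents support none of these as a general statement. They need six pairs, which the SAP does not specify. The 85% also needs 0.51 read as f in its most favourable pattern, although the protocol calls it d. With three comparisons the best case is 91%: 4 points short, and a 9% miss rate, under twice the stated 5%. If 95% is taken as the omnibus power at N = 56 (f = 0.575, not the printed 0.51), the extreme pair has 94% power over six pairs and 96% over three.

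**70 were randomised, and 56 is a minimum.** This also stands as a limit on the point. It does not rescue the statement, which is made for 14 per group, and the text does not confirm equal arms or complete follow-up.

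**The root problem is the 0.51.** Agreed that it is the larger defect. Relabelling the effect size would still leave the alpha mismatch, as Step 3 shows.

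**Conclusion.** The point holds. The stated power uses an uncorrected 0.05, while the SAP's only route to naming a differing technique is a Bonferroni-corrected comparison. With the printed 0.51 and 14 per arm, every reading tried falls below 95% after correction. Granting the contrast its 95% at 0.05 costs about 7 points with three comparisons and 13 with six.

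Two limits apply. The spread of the corrected figures comes mainly from the undefined 0.51, so no single value can be given as the trial's true pairwise power. Nor should a reader infer that the 95% is sound apart from the correction, since most readings miss it beforehand. The results rest on normal data, equal variances and two-sided tests, with a pooled error term for the t-based figures. The SAP also allows Kruskal–Wallis, for which the figures would differ. The documents do not show that the trial as enrolled misses 95% under every reading: at 17.5 per arm with three comparisons, the most favourable one reaches 96%.

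**What to change.** Keep the sample size and the analysis, and amend 'Sample size calculation':

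1. Withdraw the 95% as a statement about pairwise technique comparisons.
2. Say which effect metric and which test the 0.51 refers to, and restate the power it gives at 56.
3. State the number of Bonferroni comparisons, in the SAP as well.
4. Report the detectable difference at the corrected alpha. For six pairs: with 14 per group, a pairwise comparison at 0.0083 has 80% power for a standardised difference of 1.36 and 95% power for 1.68. The figures at 17 per group are 1.23 and 1.51, applicable if the 70 randomised are in roughly equal arms and all analysed. If three comparisons are meant, recompute at 0.0167.
5. Note that these figures assume normal data and that rank tests would differ.

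In the report, do not present a non-significant pair as evidence of no difference at 95% power.

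The cost is a few sentences and a less favourable stated power. No additional patients are needed.

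### The claimed 95% power at 56 patients (14 per group) does not follow from an effect size of d = 0.51 for the planned four-group comparison of lesion volume

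*Protocol*

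**What the plan says.** The protocol, under Sample size calculation, gives the origin of the effect size: "The effect size was calculated based on chi-square analysis data between the control group and the laser group" of an earlier study. It then labels the result: "An effect size of 0.51 Cohen d value was found to be sufficient for significance". The conclusion is introduced by "With a type 1 error of 0.05" and reads "at least 56 subjects were required for a total of 4 groups, 14 in each study group, with 95% power". The paragraph does not name the test being powered, the endpoint, the sidedness, the source rates, any conversion between effect-size scales, or an allowance for loss.

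Under Patient Recruitment and Randomization, the number actually allocated is larger: "70 patients were randomly divided into four groups". No loss rate links 56 to 70.

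The SAP, under Statistical analysis, describes the between-group comparison: "To compare lesion volume measurements according to study group at different measurement times, ANOVA and the Kruskal–Wallis test were applied", followed by Bonferroni-corrected comparisons between groups. For change over time it says: "Wilcoxon signed rank tests were used to compare lesion volume measurements according to different measurement times in the study groups". The only chi-square test in the SAP concerns sex.

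**The concern.** Three things do not fit together. The source of the effect size is categorical data from two groups. The label, Cohen d, belongs to a difference between two means. The design has four groups, compared on a continuous volume. A d of 0.51 is a moderate difference, and 14 per group is far too few to detect it with 95% power in an ordinary two-group or four-group comparison.

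This is the only power statement in the plan. Without knowing what 0.51 is, a reader cannot tell whether the trial was sized for the comparison of techniques that its title describes. Nor can a reader judge how much weight a non-significant result should carry.

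**Working it through.** **Inputs.** From the protocol: alpha 0.05, effect size 0.51, four equal groups of 14 (N = 56), claimed power 95%, 70 randomised. From the SAP: one-way ANOVA or Kruskal–Wallis across four groups. Assumptions: normal data with a common SD, two-sided tests where sidedness applies, and all six pairs tested post hoc.

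**Formulas.** One-way ANOVA: power = P(F′ > F₀.₉₅), where F′ is noncentral F with 3 and N − 4 df and λ = f²N. At N = 56 the critical value is 2.783. Chi-square: noncentral chi-square with λ = w²N. Two-sample t: noncentral t with noncentrality d√(n/2).

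**1. 0.51 as labelled (Cohen d).** Take d as the difference between the extreme groups. The value of f then depends on where the other two means lie:
- other two midway: f = 0.51 × √(1/8) = 0.180, λ = 1.82, power 16.8%
- equally spaced means: f = 0.190, power 18.3%
- one group differs from three: f = 0.51 × √3/4 = 0.221, power 23.6%
- two groups against two: f = 0.51/2 = 0.255, λ = 3.64, power 30.7%

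Reaching 95% takes 67 to 134 per group. For one unadjusted pair of 14 against 14, power is 25.5%, and 95% needs 101 per group. Kruskal–Wallis, simulated with normal data, gives about 15% to 28%.

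**2. 0.51 relabelled.**

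| Reading of 0.51 | Power at 56 | N for 95% | Power at 70 | Power at 63 (10% lost, assumed) |
|---|---|---|---|---|
| d, four-group ANOVA | 17–31% | 268–536 | 20–38% | not computed |
| Cohen's f, ANOVA | 88.4% | 72 | 95.0% | 92.3% |
| w, chi-square, 3 df | 90.8% | 67 | 96.1% | 94.0% |

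For f, λ = 0.51² × 56 = 14.57.

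**3. Routes that do reach 95% at 56.** The search was widened to see what could have produced the figure.
- *Phi converted to f.* If 0.51 is phi from the two-group table, d = 2 × 0.51/√(1 − 0.51²) = 1.186. With two arms equal to control and two equal to laser, f = 1.186/2 = 0.593. Power is 94.6% at 52 and 96.1% at 56, so 56 is the smallest balanced size. Other patterns of means give f = 0.419 to 0.514 and 72% to 89% at 56.
- *Repeated-measures ANOVA, between-groups test.* With two time points, 0.51 read as f and a correlation of 0.5, λ = f²N × 2/(1 + 0.5) and power at 56 is 95.9%. At a correlation of 0.7 it is 93.2%. The SAP does not run this test.
- *Pooled before–after test.* With 0.51 as a paired d and a signed-rank test on all patients together (efficiency 3/π relative to the t test), the smallest N is 55 and 56 gives 95.5%. A repeated-measures test of the time effect gives a similar 96.3%, with a correlation of 0.5 and f = 0.255. Neither compares techniques. In one group of 14, as the SAP applies the signed-rank test, power is 40.5%.
- *One 2×2 table of all 56.* With w = 0.51 and 1 df, power is 96.8%, but this is a two-group design.

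**4. What 14 per group can detect, whatever 0.51 was.** The omnibus ANOVA has 95% power at f of about 0.575. A Bonferroni-adjusted pair (alpha 0.05/6) has 80% power at a difference of about 1.36 SD using the pooled error, or 1.41 SD using only the two groups' data.

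**The case against.** The strongest reply is that neither document names a primary endpoint or says that 56 was sized for the four-group volume test. Failing to reproduce 56 for that test would then show incomplete reporting, not an arithmetic error. The pooled signed-rank route keeps the d label, uses a test the SAP names and needs 55, which rounds up to 56 in four equal groups. The phi route also gives 56 as the smallest balanced size for the very ANOVA in question. The d label is the least reliable input, since the text says the figure came from a chi-square, so 17% to 31% should not be read as the trial's known power. The rates behind 0.51 are in a source not available here.

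Much of this stands as a limit on the finding. It cannot be said that 56 is unobtainable or that any one power figure is the true one. The f and w shortfalls largely close if all 70 are analysed. Sidedness is also irrelevant to an omnibus F, Kruskal–Wallis or 3-df chi-square test.

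It does not remove the point. The paragraph sizes four groups, and the SAP's comparison of four groups on volume is ANOVA or Kruskal–Wallis. Each route to 95% needs a conversion, a pattern of means, a correlation, a pooling or a test that the documents do not give. The pooled signed-rank route also answers a different question from which technique heals better. That several incompatible routes land at or near 56 shows that the paragraph does not identify its own calculation.

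**Conclusion.** The concern holds. As written, the stated inputs do not deliver 95% power at 56 for the four-group comparison of lesion volume. Under the stated label the shortfall is more than 60 percentage points (17% to 31% against 95%). Under the two nearest relabellings it is about 4 to 7 points (90.8% and 88.4%). Across all readings of 0.51 considered for the ANOVA, power at 56 runs from 17% to 96%. That range measures what the paragraph leaves undetermined; it is not an estimate of the trial's power.

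At 70 analysed, the f and w readings reach about 95% and 96%, but the d reading stays at 20% to 38%. These figures rest on normal data with a common SD and, for d, on 0.51 being the largest difference among the four means. This should be fixed: it is the plan's only power claim and it is cheap to correct.

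**What to change.** Rewrite the sample size paragraph for the planned four-group volume test. State:
- the test and endpoint that 56 was meant to serve, with sidedness if that test has a direction
- whether 0.51 is d, f, w or phi, the source data it came from, and every conversion or assumption used (pattern of the four means, correlation)
- the power at 56 and at the 70 randomised under the correctly named effect size, in place of the unqualified 95%; 88% should be stated only if 0.51 is confirmed to be Cohen's f
- what 14 per group can detect: f of about 0.575 for 95% omnibus power, and about 1.36 SD for a Bonferroni-adjusted pair at 80% power (six pairs, pooled error)

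The cost is one reworded paragraph. The number randomised and the planned tests stay as they are. The stated power may turn out less favourable than the present text claims.

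### Do titles that name large lesions, with no lesion-size rule in the written eligibility, call for a change to the plan?

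*Protocol*

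**What the plan says.** The protocol title refers to "Periapical Healing of Large Periapical Lesions", and the SAP carries the same title: "Association between the Irrigation-Agitation Techniques and Periapical Healing of Large Periapical Lesions". Neither document defines the adjective.

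Eligibility is set out in the protocol under Patient Recruitment and Randomization. The rule about the lesion is: "The study included mandibular single-rooted teeth that were diagnosed with asymptomatic apical periodontitis and had a periapical index (PAI) score of 3 or higher". The remaining criteria concern age, general health, medication and other features of the tooth. Some carry numeric cut-offs, for example the exclusion of "patients with teeth with a periodontal pocket depth of 5 mm or more". None gives a lesion dimension.

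On screening, the protocol states: "A total of 97 patients aged 18-65 were evaluated radiographically and clinically for conformity with the inclusion and exclusion criteria". Of these, 70 were randomised. CBCT imaging "was requested for patients who met the study criteria before the procedure to obtain information about periapical lesion size", among other purposes.

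Lesion volume then becomes the outcome measurement. Under Healing evaluation: "The volume data were compared with the preoperative CBCT measurements for each patient". The SAP (Statistical analysis) uses ANOVA and Kruskal–Wallis tests "To compare lesion volume measurements according to study group at different measurement times", Wilcoxon signed-rank tests within groups, and Spearman correlations with age.

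**The concern.** A title is where most readers learn who a trial is about. Here it promises large lesions, while the written rules admit any qualifying tooth that reaches a minimum periapical index score. The same paragraph gives thresholds for mobility and pocket depth, so the absence of one for the feature in the title stands out. CBCT, the imaging that would show size in three dimensions, is requested only for patients who have already met the criteria, so on the written sequence it does not select anyone.

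What would be at stake is applicability. If the relative benefit of an agitation technique depends on lesion size, an average over all lesions at or above the entry score could differ from the effect in large lesions alone. A reader relying on the title would then carry the result to a population that the rules do not guarantee.

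**Working it through.** The plan states no figure on this point that could be reproduced, so the check is mainly a comparison of passages.

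1. **Where the adjective is used.** It describes the lesions in the two titles only. The sample-size section, eligibility paragraph, follow-up section, volume-measurement section and statistical analysis never rely on it.

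2. **What the entry rule says about extent.** It sets a minimum periapical index score. The documents do not translate any score into millimetres or cubic millimetres. An implied size floor can therefore be neither confirmed nor ruled out, and it would be wrong to treat the index as unrelated to size.

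3. **Whether size could have selected patients.** The written sequence rules out CBCT as a selection step, because it follows eligibility. It does not rule out a judgement made on the images used at screening, which was both radiographic and clinical. The flow diagram (Figure 1), where reasons for non-entry would normally be listed, is not reproduced in the text available. The number not randomised is 97 − 70 = 27, and 27 / 97 = 27.8%. How many of the 27, if any, were set aside for lesion size cannot be seen.

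4. **What follows in each case.**
   - *A size judgement was applied.* The title is accurate and the eligibility text omits one line.
   - *No size judgement was applied.* The title is loose, and the population is the one stated in the eligibility paragraph.

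   In both cases the same 70 patients are randomised, the same volumes are measured and the same tests are run. One set of entry rules applies to all four groups before allocation, so neither case introduces a difference between groups.

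5. **Whether a reader is left without the facts.** Volumes are obtained in mm³ before treatment and at one year, and the SAP compares them by group at each measurement time, which includes baseline. The plan does not promise a descriptive baseline table. Even so, summarising the baseline volumes that are being compared is ordinary practice, and those figures tell a reader how large the lesions were better than any adjective could.

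6. **Magnitude.** The proportion of lesions that are not large needs both a definition and a baseline distribution. The documents give neither, so no figure or defensible range can be offered.

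**The case for a change.** The strongest opposing case is that the wording is plainly mismatched and cheap to put right. The criteria read as a full list, and screening is described as checking conformity with that list, so a reader is entitled to assume that no unwritten size rule existed. The authors wrote thresholds elsewhere in the same paragraph. The population named in the title is also the one to which clinicians will apply the result, so calling it only a title understates its influence.

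Part of this stands. Neither document supports the adjective, and the eligibility paragraph is the safer description of who was studied. A conclusion confined to large lesions would need a definition that the plan does not supply.

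The step from there to a required change does not stand. The supplied text makes no claim of an effect specific to large lesions, so the harm depends on how a later report is worded and read. Removing the adjective without knowing what was done at screening could itself misdescribe the population: if a size judgement was made, deletion would suggest that all lesions at or above the entry score were accepted. Deletion would also widen the population described. Neither choice of wording alters the design, the data or any analysis.

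**Conclusion.** The observation is correct as a matter of text: the titles say large, and the readable eligibility rules neither define the word nor set a lesion dimension. It is a low-severity clarification about labelling and does not warrant a change to the plan. The effect on the randomised comparison is nil. The effect on applicability cannot be quantified from these documents and is limited by the explicit entry rule and by the measured baseline volumes.

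This rests on three assumptions: that the written criteria were applied alike before allocation, as the protocol describes; that those reporting the trial will describe the enrolled population by its entry criteria and summarise the baseline volumes, as analysts ordinarily do; and that no conclusion specific to large lesions is drawn without a stated definition. It does not assume that the enrolled lesions were large or that they were small, because the documents settle neither.
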